1 SYNOPSIS

Protocol Title: A Phase 1/2 Dose Escalation and Combination Cohort Study to Evaluate the Safety and Tolerability, Pharmacokinetics, and Efficacy of BMS-986226 (anti-ICOS mAb) Alone or in Combination with Nivolumab or Ipilimumab in Patients with Advanced Solid Tumors

Study Phase: 1/2

Rationale:

Subsequent to the approval of cytotoxic T lymphocyte-associated antigen-4 (CTLA-4) and programmed death-1 (PD-1) pathway-blocking agents as anti-tumor therapies, the field of tumor immunotherapy is expanding rapidly. In addition to blocking co-inhibitory pathways, activating co-stimulatory pathways with the goal of potentiating anti-tumor immune responses are now considered a promising additional approach. With recent emerging clinical evidence that supports the significant anti-tumor activity of single-agent immunotherapies, combination therapies are now explored in an attempt to increase overall patient survival as exemplified by the combination therapy of anti-PD-1 and anti-CTLA-4 antibodies in patients with advanced melanoma. These findings raise the possibility that combining checkpoint blocking antibodies with agonistic antibodies that target T-cell co-stimulatory molecules could also be beneficial.

In this study, participants with advanced tumors will be treated with BMS-986226 (an agonistic antibody targeting inducible T-cell co-stimulator [ICOS]) in monotherapy or in combination with nivolumab (BMS-936558, PD-1 receptor blocking monoclonal antibody [mAb]) or ipilimumab (BMS-734016/MDX010; a checkpoint blocking antibody that recognizes CTLA-4).

Research hypothesis:

It is anticipated that BMS-986226, anti-ICOS mAb, administered as single agent or in combination with nivolumab (BMS-936558/MDX, anti-PD-1 antibody) or ipilimumab (BMS-734016/MDX, anti-CTLA-4 antibody), will demonstrate acceptable safety and tolerability and a favorable risk/benefit profile that will support further clinical testing. No prospective hypotheses are being formally evaluated in this study.

Study Population:

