5.1.2.1 Monotherapy Dose Escalation (Preliminary Safety Cohorts and Part A)

Up to approximately 34 participants may be treated during the monotherapy dose escalation (Preliminary Safety Cohorts and Part A).

Expected dose levels for monotherapy dose escalation (Preliminary Safety Cohorts and Part A) are provided in Table 5.1.2.1-1. All participants treated with BMS-986226 monotherapy are recommended to receive premedications, as described in Section 7.1, in order to reduce the risk of infusion-related reactions.

Preliminary Safety Cohorts

The Preliminary Safety Cohorts will evaluate the safety of BMS-986226 following monotherapy administration of 2 dose levels, 2 mg and 8 mg.

A single new participant per cohort will be administered an IV BMS-986226 as follows:

- BMS-986226 2 mg Q4W in 4-week cycles for up to 24 weeks of study treatment
- BMS-986226 8 mg Q4W in 4-week cycles for up to 24 weeks of study treatment

For the purpose of guiding dose escalation, dose-limiting toxicities (DLTs) will be defined based on the incidence, intensity, and duration of AEs for which no clear alternative cause is identified. The DLT period will be 28 days (4 weeks) in the Preliminary Safety Cohorts. Any toxicities that occur beyond the 4-week DLT period will also be considered in dose-level decisions. For the purpose of participant management, any AE that meets DLT criteria (Section 7.3.2), regardless of the cycle in which it occurs, will lead to discontinuation of study treatment. Participants who discontinue study treatment during the 4-week DLT evaluation period for reasons other than a DLT may be replaced with a new participant at the same dose level. AEs will be graded according to the National Cancer Institute (NCI) Common Terminology Criteria for Adverse Events (CTCAE) v4.03²⁷.

Once the safety (during the 4 weeks DLT period) of 2 mg and 8 mg of BMS-986226 has been established in a single, independent participant per dose, Part A will start.

Additional participants may be enrolled in the Preliminary Safety Cohorts per dose level as early as 5 days after the first participant is treated at each dose level to gather additional information on the safety, PK, and PD profile.

Intra-participant dose escalation is only allowed in the Preliminary Safety Cohorts as follows:

- Once the observation period of 4 weeks for 8 mg is completed, participant(s) treated at 2 mg may be offered the possibility to dose escalate at 8 mg.

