During the dose-escalation phase, a set of approximately 3 participants will be treated initially at each specified dose level. Cohort tolerability assessment and subsequent dose recommendation will occur when at least 2 evaluable participants within a cohort have completed a 5-week DLT period. Any toxicities that occur beyond the 5-week DLT period will be accounted for in making dose level decisions and/or dose level modifications.

If the potential DLT occurring in the third evaluable participant regarding the specific dose level does not influence the dose recommendation by BLRM, the next dose level may proceed without waiting for the third participant to complete the corresponding DLT observation period after discussion and agreement between the Sponsor and investigators. Continuous re-assessment of dose recommendation, by BLRM in the monotherapy escalation phase, will be carried out for each dose level. Planned dose levels for dose escalation are provided in Table 5.1.2.1-1. Planned dose levels may be modified, or additional intermediate dose levels added, based upon the BLRM

analysis. Once the safety (during the DLT evaluation) of a monotherapy dose level has been established (Preliminary Safety Cohorts and Part A), additional participants (up to 12 total) may be added at that dose level to better characterize the safety, PK, and PD profile.

Dose Level	BMS-986226		
1	2 mg (Preliminary Safety Cohorts)		
2	8 mg (Preliminary Safety Cohorts)		
3	25 mg (Part A)		
4	80 mg (Part A)		
5	200 mg (Part A)		
6	400 mg (Part A)		
7	800 mg (Part A)		

 Table 5.1.2.1-1:
 Dose Escalation (Preliminary Safety Cohorts and Part A)

Dose-limiting Toxicities in Part A

For the purpose of guiding dose escalation, DLTs will be defined based on the incidence, intensity, and duration of AEs for which no clear alternative cause is identified. The DLT period will be 35 days (5 weeks) in Part A. Any toxicities that occur beyond the 5-week DLT period will also be considered in dose-level decisions.

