7.3.2 BMS-986226 Dose-limiting Toxicities

For the purpose of guiding dose escalation, DLTs will be defined based on the incidence, intensity, and duration of AEs for which no clear alternative cause is identified. The DLT period will be 35 days (5 weeks).

In the Preliminary Safety Cohorts, participants who have received 1 dose of BMS-986226 and have completed, or who discontinued due to a DLT in the 4-week DLT period, will be considered as DLT-evaluable participants for BMS-986226 monotherapy.

In Part A, participants who have received 2 doses of BMS-986226 and have completed, or who discontinued due to a DLT in the 5-week DLT period, will be considered as DLT-evaluable participants for BMS-986226 monotherapy.

In Parts B, C, D and E, participants receiving either 1 dose of BMS-986226 or 2 doses of either nivolumab or ipilimumab, or participants who discontinued due to a DLT in the 5-week combination treatment DLT period, will be considered as DLT-evaluable participants for combination treatment. Participants who withdraw from the study during the DLT evaluation period or have received less than 2 doses for reasons other than a DLT in the monotherapy (Part A) or 1 dose in combination therapy (Parts B, C, D, E), will not be considered as DLT-evaluable participants in Part A, who are dose delayed during the DLT evaluation period for reasons other than a DLT could be considered as DLT-evaluable participants if they receive at least 2 doses of therapy.

For the purpose of participant management, any AE that meets DLT criteria, regardless of the cycle in which it occurs, will lead to discontinuation of study treatment (except as defined in Section 7.3.5). Participants who withdraw from the study during the 5-week DLT evaluation period for reasons other than a DLT may be replaced with a new participant at the same dose

level. The incidence of DLT(s) during the 5-week DLT evaluation period will be used in dose escalation decisions through application of the BLRM/BLRM-Copula model. AEs occurring after the DLT period will be considered to enhance the robustness of BLRM/BLRM-Copula prediction, upon agreement between the Sponsor, Medical Monitor/Study Director (or designee), and investigators.

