Participants experiencing a DLT will enter the safety follow-up period of the study. DLTs occurring after the 4-week DLT observation period for the Preliminary Safety Cohorts or 5-week DLT observation period for Parts A, B and C will be accounted for in determining the MAD for the combination part.

AEs will be graded according to the NCI CTCAE v4.03²⁷, as listed below:

A. Hepatic Non-hematological DLT

Any one of the following study treatment-related events will be considered a hepatic DLT:

- Any Grade \geq 3 elevation of AST, ALT, or total bilirubin.
- Grade 2 AST or ALT with symptomatic liver inflammation (eg, right upper quadrant tenderness, jaundice, pruritus).
- AST or ALT > 3× ULN and concurrent total bilirubin > 2× ULN without initial findings of cholestasis (elevated serum alkaline phosphatase [ALP] [eg, findings consistent with Hy's law or FDA definition of potential drug-induced liver injury or potential drug-induced liver injury [p-DILI]). Note that this special category of DLT uses ULN rather than Common Toxicity Criteria (CTC) grade for definition.

B. Non-hepatic Non-hematological DLT

Any of the following events will be considered a non-hepatic non-hematological DLT:

- Any Grade 2 drug-related uveitis or eye pain or blurred vision that does not respond to topical therapy and does not improve to Grade 1 severity ≤ 2 weeks *or* requires systemic treatment.
- Grade 3 drug-related uveitis, pneumonitis, bronchospasm, myocarditis, neurologic toxicity, hypersensitivity reaction, or infusion reaction of any duration will require discontinuation.
- Any Grade 3 or greater nondermatologic, nonhepatic nonhematological study treatment-related toxicity will be considered a DLT, with the following specific exceptions:
 - Grade 3 or Grade 4 electrolyte abnormalities that are not complicated by associated clinical adverse experiences, last \leq 72 hours, and either resolve spontaneously or respond to conventional medical intervention
 - Grade 3 nausea, vomiting, or diarrhea that lasts less than 72 hours (without steroid therapy) and either resolves spontaneously or responds to conventional medical intervention
 - Isolated Grade 3 elevation of amylase or lipase not associated with clinical or radiographic evidence of pancreatitis

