 - Isolated Grade 3 fever not associated with hemodynamic compromise (eg, hypotension, clinical or laboratory evidence of impaired end-organ perfusion or with other symptoms of infusion-related reactions that returns to ≤ Grade 1 with standard treatment in ≤ 1 hour

Revised Protocol No.: 04 Date: 31-May-2019

- Grade 3 endocrinopathy that is well controlled by hormone replacement
- Grade 3 tumor flare (defined as pain, irritation, or rash that localizes to sites of known or suspected tumor)
- Grade 3 fatigue for \leq 7 days
- Grade 3 infusion reaction that returns to Grade 1 in \leq 1 hour

C. Dermatologic DLT

- Grade 3/4 rash if no improvement (ie, resolution to Grade ≤ 1) after a 1-week to 2-week infusion delay. Participants who have not experienced a Grade 3 drug-related skin AE may resume treatment in the presence of Grade 2 skin toxicity.
- Grade 4 rash of any duration

D. Hematologic DLT

- Grade 4 neutropenia \geq 5 days in duration
- Grade 4 thrombocytopenia or Grade 3 thrombocytopenia with clinically significant bleeding or any requirement for platelet transfusion
- Grade 4 anemia not explained by underlying disease
- Grade 4 febrile neutropenia
- Grade 3 febrile neutropenia that lasts > 48 hours
- Grade \geq 3 hemolysis (i.e., requiring transfusion or medical intervention such as steroids)

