Patients on IV steroids may be switched to an equivalent dose of oral corticosteroids (e.g. prednisone) at start of tapering or earlier, once sustained clinical improvement is observed. Lower bioavailability of oral corticosteroids should be taken into account when switching to the equivalent dose of oral corticosteroids.

Hepatic Adverse Event Management Algorithm

Rule out non-inflammatory causes. If non-inflammatory cause, treat accordingly and continue I-O therapy. Consider imaging for obstruction.

Patients on IV steroids may be switched to an equivalent dose of oral corticosteroids (e.g. prednisone) at start of tapering or earlier, once sustained clinical improvement is observed. Lower bioavailability of oral corticosteroids should be taken into account when switching to the equivalent dose of oral corticosteroids.

*The recommended starting dose for grade 4 hepatitis is 2 mg/kg/day methylprednisolone IV.

27-Jun-2018

Refer to http://livertox.nih.gov/ for a compendium of agents that may cause liver injury

Endocrinopathy Adverse Event Management Algorithm

Rule out non-inflammatory causes. If non-inflammatory cause, treat accordingly and continue I-O therapy. Consider visual field testing, endocrinology consultation, and imaging.

Patients on IV steroids may be switched to an equivalent dose of oral corticosteroids (e.g. prednisone) at start of tapering or earlier, once sustained clinical improvement is observed. Lower bioavailability of oral corticosteroids should be taken into account when switching to the equivalent dose of oral corticosteroids.

27-Jun-2018

Skin Adverse Event Management Algorithm

Rule out non-inflammatory causes. If non-inflammatory cause, treat accordingly and continue I-O therapy.

Patients on IV steroids may be switched to an equivalent dose of oral corticosteroids (e.g. prednisone) at start of tapering or earlier, once sustained clinical improvement is observed. Lower bioavailability of oral corticosteroids should be taken into account when switching to the equivalent dose of oral corticosteroids. *Refer to NCI CTCAE v4 for term-specific grading criteria.

^If SJS/TEN is suspected, withhold I-O therapy and refer patient for specialized care for assessment and treatment. If SJS or TEN is diagnosed, permanently discontinue I-O therapy.

Neurological Adverse Event Management Algorithm

Rule out non-inflammatory causes. If non-inflammatory cause, treat accordingly and continue I-O therapy.

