2 DECISION RULE FOR DOSE ESCALATION AND SIMULATION

Dose escalation recommendations for BMS-986226 monotherapy will be based on the inference from the Bayesian posterior and the probability that the true DLT rate for each dose lies in 1 of the following categories:

- [0%, 16%) under-dosing
- [16%, 33%) targeted toxicity
- [33%, 100%] excessive toxicity

Note: "[" or "]" is inclusive of the respective endpoint, and "(" or ")" exclusive of the respective endpoint.

These boundaries are similar to the toxicity boundaries used by a rule-based design (ie, 3 + 3 design) in that a minimum is set at 16% (~ 1 in 6) DLT rate and a maximum at 33% (~ 2 in 6) DLT rate. Following the principle of EWOC, dose recommendations for the next cohort will be based on the Bayesian model after DLT information becomes available during the DLT period, accounting for all of the available data from the administered doses, and the candidate doses are the ones fulfilling the overdose criterion that there is less than 30% chance of excessive toxicity. Only the candidate doses will be considered for the next cohort. While the Bayesian model will use DLT information from the DLT period only, clinical assessment will take into consideration of the totality of available data including pharmacokinetics (PK)/pharmacodynamics from all treated participants.

Stopping Rules:

The following is the general stopping rules of BLRM (-Copula) during Dose Escalation:

• If all of 30 DLT evaluable participants are treated.

- If all of the current pre-specified doses are considered intolerable according to the pre-specified cutoff (ie, EWOC criteria), then the model will recommend stopping the current dose level and a new dose level lower than the current lowest dose level will need to be identified.
- The maximum number of DLT-evaluable participants in a dose level will be 12. This limit is set to avoid instances in which the model could recommend adding subjects indefinitely to a specific dose level due to uncertainty in the tolerability profile.
- If, for a specific dose level, 6 subjects have been treated and the chance of determining that the dose level to be the "target" dose is > 50%, then the model will suggest to stop and declare the current dose level to be the maximum tolerated dose (MTD).

Model-recommended MTD:

The MTD is the dose that satisfies the following 3 conditions:

- 1) The empirical posterior probability that the 'DLT rate of 16% -< 33%' is greater than 50%.

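### DLT categories A to D in Section 7.3.2 leave some severe skin and hepatic toxicity without a criterion, and the rule for counting Grade 3 rash within the DLT window is undefined

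*Combined protocol and SAP*

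**What the plan says.** Section 7.3.2 defines DLTs in four categories.

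- **A (hepatic):** criteria based on AST, ALT and total bilirubin only.
- **B (non-hepatic, non-hematological):** named events, including Grade 3 hypersensitivity, and then a general rule: "Any Grade 3 or greater nondermatologic, nonhepatic nonhematological study treatment-related toxicity will be considered a DLT", with listed exceptions.
- **C (dermatologic):** Grade 3/4 rash that has not resolved to Grade 1 or less "after a 1-week to 2-week infusion delay", and Grade 4 rash of any duration. No other skin event is listed.
- **D (hematologic):** a list of specific events.

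Appendix 6, in the skin algorithm, says: "If SJS or TEN is diagnosed, permanently discontinue I-O therapy".

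On the window, Section 5.1.2.1 says "The DLT period will be 35 days (5 weeks) in Part A", and for the first two dose levels "The DLT period will be 28 days (4 weeks) in the Preliminary Safety Cohorts". Parts B and C also use 35 days.

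On what the model uses, Appendix 10 Section 2 says "While the Bayesian model will use DLT information from the DLT period only", adding that clinical assessment looks at all available data. Section 10.1.1 and Appendix 10 Section 5 say the same. Sections 5.1.2.1 and 7.3.2, however, allow AEs after the window to be considered for the BLRM or BLRM-Copula when sponsor and investigators agree.

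**The concern.** B's general rule hands skin and hepatic events over to other categories, but A and C pick up only part of what is handed over. What remains is not a DLT by definition, however severe. In Part A such an event can be lost twice. A participant stopped before dose 2 for something that is not a DLT is not DLT-evaluable and may be replaced, so neither the event nor the participant reaches the model.

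The rash criterion raises a different problem. Whether an event has qualified depends on a delay with no stated start, judged against a window of fixed length.

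The stake is dose escalation. DLT counts are the toxicity input to the BLRM and BLRM-Copula, cohorts are about 3 participants in Part A, and Section 5.1.6 provides no data monitoring committee. One event counted or not can change the model's output.

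**Working it through.** **1. Coverage of A to D.** Take a drug-related Grade 3-4 skin event that is not a rash. A does not apply. B's general rule does not apply, because the event is dermatologic. B's named events apply only if it is classed as hypersensitivity (or another listed term). C does not apply, because it lists only rash. D does not apply. No criterion is met. The same steps place a Grade 3 or higher hepatic event outside the AST, ALT and bilirubin criteria in neither A nor B.

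**2. Timing of the rash criterion.** Inputs: first dose on Day 1; 28-day cycles (Section 5.1.2); windows of 35 and 28 days.

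*Reading 1, delay of the next scheduled infusion:*

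- Q4W infusion due on Day 1 + 28 = 29. A 1-week delay ends on Day 29 + 7 = 36 and a 2-week delay on Day 29 + 14 = 43. Both fall after Day 35, the first by one day.
- Parts B1/C1: BMS-986226 is next due on Day 1 + 84 = 85, so the delay ends on Day 92 to 99. The partner drug is due on Day 29, so Day 36 to 43 again.
- Preliminary Safety Cohorts: the window closes on Day 28, before a second infusion falls due.

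*Reading 2, hold counted from rash onset:*

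- 35-day window: a 1-week hold finishes in time for onset up to Day 35 - 7 = 28, and a 2-week hold for onset up to Day 35 - 14 = 21.
- 28-day window: onset up to Day 21 and Day 14.

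Sections 7.3.1 to 7.3.4 do not choose between the readings. They also do not say whether a DLT is dated by onset or by the day it qualifies.

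**3. Effect of one uncounted event.** Model (Appendix 10, Sections 1.1, 1.2 and 2): logit(p) = log(α) + β·log(dose/800), with log(α) ~ N(-0.847, SD 1.53), log(β) ~ N(0, SD 1) and correlation 0. A dose is a candidate if P(DLT rate ≥ 33%) < 0.30. The candidate with the highest P(16% to < 33%) is recommended. I computed the posterior by grid integration.

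First, the plan's own example in Appendix 10 Section 3 (0/3 at 25 mg, 1/3 at 80 mg). Stated target probabilities are 0.372 at 200 mg and 0.311 at 80 mg; I obtain 0.360 and 0.299. Overdose probabilities are 0.284 at 200 mg, 0.468 at 400 mg and 0.63 at 800 mg. The exclusions and the 200 mg recommendation match the plan.

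Then 0/3 at each of 25, 80 and 200 mg, with one event among 3 participants at 400 mg:

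| Entry at 400 mg | P(overdose) at 800 mg | Raw model output |
|---|---|---|
| 1/3 (counted) | about 0.47 | stay at 400 mg |
| 0/3 (not counted) | about 0.22 | 800 mg |
| 0/2 (participant dropped) | about 0.24 | 800 mg |

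In the plan's 80 mg example, changing 1/3 to 0/3 or 0/2 lowers the overdose probability at 400 mg from 0.468 to 0.113 or 0.128. The raw output moves from 200 mg to 400 mg, one planned level. These are model outputs, not dose recommendations.

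**The case against.** The strongest reply concerns Grade 3 rash. Other DLT criteria also have a waiting time, such as Grade 4 neutropenia lasting at least 5 days. Section 7.3.4 withholds treatment for a potential DLT while it is assessed, so later adjudication is expected. Later toxicity is considered in dose-level decisions (Section 5.1.2.1) and in setting the maximum administered dose for the combination part (Section 7.3.2). The primary endpoint of AEs meeting DLT criteria states no 35-day limit, so a rash qualifying on Day 36 still counts there. All of this stands. A reader might infer that Grade 3 rash can never qualify inside the window and is certain to be lost to the model. The documents do not support that: it needs Reading 1, dating by the day of qualification, and no agreement to use later data.

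A reader might also infer that SJS/TEN certainly falls in the gap. That depends on how the event is coded; it might be classed as rash or hypersensitivity, and the grading definitions are not in the documents. It is a possible example only. Appendix 6 shows a treatment-ending rule for SJS/TEN, not for Grade 3 rash.

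On evaluability, Section 7.3.2 says that delayed Part A participants could still be evaluable if they receive 2 doses. Only the status while the rash is unresolved is unclear, including after a delay of more than 12 days, which Section 7.3.1 treats as a missed dose.

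None of this answers the coverage gap. Holding treatment does not make an event a DLT, and the routes for later or unlisted events depend on agreement or judgment.

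**Conclusion.** The coverage gap holds under every reading of the timing: B excludes skin and hepatic toxicity more broadly than A and C take it up. For Grade 3 rash the defect is an undefined counting rule rather than certain loss. The delay has no stated start, DLTs have no dating rule, and the documents conflict on whether later events reach the model.

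The size is conditional. If one such event occurs at 400 mg after clean cohorts, whether it is counted puts the overdose probability at 800 mg above or below the 0.30 cap (about 0.47 against 0.22 to 0.24). That rests on the stated prior, cohorts of 3 and a hypothetical history. It shows the effect of any uncounted event. The documents give no frequency for these events, and the safety summary in Section 3.2.2.4 mentions no rash. This should be fixed; it does not show that any escalation decision has been wrong.

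**What to change.** Amend Section 7.3.2 so that B's general rule excludes only events that A, C or D actually address, including events for which those categories set a threshold. If the sponsor intends other severe skin or hepatic events not to be DLTs, the section should list them as exceptions.

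Then reconcile Sections 5.1.2.1, 7.3.1, 7.3.2, 7.3.4 and 10.1.1, Appendix 10 Sections 2 and 5, and Appendix 6 on four points:

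1. when the rash delay starts, including in the 28-day window and under Q12W dosing;
2. whether a DLT is dated by onset or by the day it qualifies;
3. whether a Part A participant is evaluable while a potential DLT is pending;
4. whether events after the window enter the model, and by what rule.

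The sponsor sets all clinical thresholds.

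The cost is a wording amendment. The downside is that some additional events may count as DLTs. Because meeting DLT criteria leads to discontinuation, subject to the exceptions in Section 7.3.5, a wider definition also affects when participants stop treatment, and the sponsor should weigh that when drafting.
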